### 8.5.2 Definition of Serious Adverse Events (SAE)

A serious adverse event (SAE) is any AE, occurring at any dose and regardless of causality that:

- Results in death
- Is life-threatening “Life-threatening” means that the patient was at immediate risk of death from the reaction as it occurred, i.e., it does not include a reaction that hypothetically might have caused death had it occurred in a more severe form.
- Requires inpatient hospitalization or prolongation of existing hospitalization (see clarification in the paragraph below on planned hospitalizations)

- Results in persistent or significant disability/incapacity “Disability” is defined as a substantial disruption of a person’s ability to conduct normal life functions.
- Is a congenital anomaly/birth defect
- Is an important medical event

An “important medical event” is an event that may not result in death, be life-threatening, or require hospitalization but may be considered an SAE when, based upon appropriate medical judgment, it may jeopardize the patient and may require medical or surgical intervention to prevent 1 of the outcomes listed in the definitions for SAEs. Examples of such medical events include allergic bronchospasm requiring intensive treatment in an emergency room or at home, blood dyscrasias or convulsions that do not result in inpatient hospitalization, or the development of drug dependency or drug abuse.

Clarification should be made between the terms “serious” and “severe” because they are not synonymous. The term “severe” is often used to describe the intensity (severity) of a specific event (as in mild, moderate, or severe myocardial infarction); however, the event itself may be of relatively minor medical significance (such as a severe headache). This is NOT the same as a “serious” adverse event (SAE), which is based on patient/event outcome or action criteria described above. An SAE is usually an event that poses a threat to a patient’s life or ability to function. In contrast, an AE assessed as “severe” is not automatically considered “serious” in nature (i.e., an SAE). For example, persistent nausea of several hours duration may be considered severe nausea but not an SAE. On the other hand, a stroke resulting in only a minor degree of disability may be considered mild, but would be defined as an SAE based on the above noted criteria. Seriousness (not severity) serves as a guide for defining regulatory reporting obligations.

Other Reportable Information: certain information, although not considered an SAE, must be recorded, reported, and followed up as indicated for an SAE. This includes:

- A case involving a pregnancy exposure to a test article, unless the product is indicated for use during pregnancy e.g., prenatal vitamins. Information about use in pregnancy encompasses the entire course of pregnancy and delivery and perinatal and neonatal outcomes, even if there were no abnormal findings. If a pregnancy is confirmed, test article must be discontinued immediately in female patients. All reports of pregnancy must be followed for information about the course of the pregnancy and delivery, as well as the condition of the newborn. When the newborn is healthy, additional follow-up is not needed. Pregnancies occurring up to 3 months after completion of the study treatment must also be reported to the investigator.
- Overdose (e.g., a dose higher than that indicated in the protocol) with or without an AE.
- Abuse (e.g., use for nonclinical reasons) with or without an AE
- Inadvertent or accidental exposure with or without an AE
- Device malfunction with or without an AE

### 8.5.3 Classification of an Adverse Event

#### 8.5.3.1 Severity of Event

The severity of AEs should be graded as follows:

- Mild – Usually transient in nature and generally not interfering with normal activities
- Moderate – Sufficiently discomforting to interfere with normal activities
- Severe – Inability to perform normal daily activities

Medically significant AEs considered related to the study drug by the investigator or Sponsor will be followed until resolved or considered stable.

It will be left to the investigator's clinical judgment to determine whether an AE is related and of sufficient severity to require the patient's removal from treatment or from the study. A patient may also voluntarily withdraw from treatment due to what he or she perceives as an intolerable AE. If either of these situations arises, the patient should be strongly encouraged to undergo an end-of-study assessment and be under medical supervision until symptoms cease or the condition becomes stable.

#### 8.5.3.2 Relationship to Study Intervention

The following AE attributes must be assigned by the investigator: AE diagnosis or syndrome(s) (if known, signs or symptoms if not known); event description (with detail appropriate to the event); dates of onset and resolution; severity; assessment of relatedness to study drug and action taken. The investigator may be asked to provide follow-up information, discharge summaries, and extracts from medical records or eCRFs.

Relatedness to study drug administration will be determined by the investigator responding to the question, 'Is there a reasonable possibility that the AE is associated with the study drug?' Relatedness to study drug administration will be graded as "related", "probably," "possibly," or "not related," as follows:

- Not Related
  - Another cause of the event is most plausible, or
  - Clinically plausible temporal sequence is inconsistent with the onset of the event and the study treatment administration, or
  - A causal relationship is considered biologically implausible.
- Possibly Related
  - An event that follows a reasonable temporal sequence from administration of the study treatment or a known or expected response pattern to the suspected drug, but that could readily have been produced by a number of other factors.

- Probably Related
  - An event that follows a reasonable temporal sequence from administration of the study treatment, and
  - There is a biologically plausible mechanism for study treatment causing or contributing to the AE, and
  - The event could not be reasonably explained by the known characteristics of the patient’s clinical state.
- Related
  - An event that occurs in a plausible time relationship to drug administration, and which cannot be explained by concurrent disease or other drugs or chemicals.
  - The response to withdrawal of the drug (dechallenge) should be clinically plausible. The event must be definitive pharmacologically or phenomenologically, using a satisfactory rechallenge procedure if necessary.

In addition, the relationship may be confirmed by improvement on stopping the study treatment and reappearance of the event on repeated exposure.

#### 8.5.3.3 Expectedness

The Sponsor will be responsible for determining whether an AE is expected or unexpected. An AE will be considered unexpected if the nature, severity, or frequency of the event is not consistent with the risk information previously described for the study intervention.

#### 8.5.4 Adverse Event Reporting

All AEs and SAEs will be collected and recorded from the time of the patient receives the first dose of study drug until the end-of-study visit for all subjects with informed consent. The Investigator will assess all AEs and SAEs and record the following information where appropriate on the CRF:

- Event description
- Date of onset
- Date of resolution or stabilization
- Assessment of severity
- Relationship to study drug
- Action taken with study medication

The Investigator should employ best medical judgment in determining how to manage AEs and SAEs. Any questions regarding AE or SAE management should be directed to the Medical Monitor.

The Sponsor will be responsible for notifying the FDA of any unexpected fatal or life-threatening suspected adverse reaction as soon as possible, but in no case later than 7 calendar days after the Sponsor's initial receipt of the information. In addition, the Sponsor must notify the FDA and all participating investigators in an IND safety report of potential serious risks, from clinical trials or any other source, as soon as possible, but in no case later than 15 calendar days after the Sponsor determines that the information qualifies for reporting.

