### **5.4 Screen Failures**

Screen failures are defined as participants who consent to participate in the clinical trial but are not subsequently randomized in the study. A minimal set of screen failure information is required to ensure transparent reporting of screen failure participants, to meet the Consolidated Standards of Reporting Trials (CONSORT) publishing requirements and to respond to queries from regulatory authorities. Minimal screening failure information includes demography, screen failure details, eligibility criteria, and any SAE.

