## **7 STUDY ACTIVITIES**

### **7.1 Screening Visit (Day -28 to -1)**

Patient's eligibility for the study will be evaluated during this period based on medical history, physical examination, including flexible proctosigmoidoscopy or colonoscopy where indicated, laboratory values and additional tests.

Patients will be screened within 28 days prior to baseline and administration of study medication to confirm that they meet the entrance criteria for the study. The study investigator or appropriate delegate at the site will discuss with each patient the nature of the study, its requirements, risks and benefits. Written informed consent must be obtained prior to performing any protocol-specific procedures, including washout of prohibited medications.

In addition to obtaining informed consent, the following procedures will be performed:

- Collection of demographic information
- Completion of medical history (including prior medication, history of alcohol and drug use, smoking status and weekly alcohol consumption)
- Vital signs (including temperature)
- Physical examination (including weight and height)
- 12-lead ECG
- Mayo score (stool frequency, rectal bleeding, endoscopic findings [flexible proctosigmoidoscopy/colonoscopy], physician's global assessment)
- Review of inclusion/exclusion criteria
- Blood sampling for clinical lab tests (serum chemistry, hematology, pregnancy, and CRP)
- Endoscopy which must be evaluated by a central reader to confirm the endoscopic sub-score for the eligibility.
- Biopsy sampling for histologic assessment and tissue concentration during the endoscopy.
- UCEIS
- Distribution of a fecal sample collection container for V2 (baseline) sample

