## **8.5 Adverse Events and Serious Adverse Events Reporting**

### 8.5.1 Definition of Adverse Events (AE)

An adverse event (AE) is any untoward medical occurrence in a patient administered a pharmaceutical product, which does not necessarily have a causal relationship with the treatment. An AE can be any unfavorable and unintended sign (e.g., including an abnormal laboratory finding), symptom, or disease temporally associated with the use of the study drug, whether or not it is considered to be study drug related. This includes any newly occurring event or previous condition that has increased in severity or frequency since the administration of study drug.

Note that progression of the ulcerative colitis investigated in this protocol, including secondary events that are subsumed under a unifying diagnosis of disease progression, will NOT be considered an AE unless the investigator judges the progression to be related to treatment with study drug.

An AE includes, but is not limited to, the following:

- Any clinically significant worsening of a pre-existing condition
- An AE occurring from overdose (i.e., a dose higher than that indicated in the protocol) of a study drug, whether accidental or intentional
- An AE occurring from abuse (e.g., use for nonclinical reasons) of a study drug
- An AE that has been associated with the discontinuation of the use of a study drug
- Any treatment-emergent abnormal laboratory result that is clinically significant, i.e., meeting 1 or more of the following conditions, should be recorded as a single diagnosis on the AE page in the eCRF:
  - Accompanied by clinical symptoms
  - Leading to a change in study medication (e.g., dose modification, interruption or permanent discontinuation)
  - Requiring a change in concomitant therapy (e.g., addition of, interruption of, discontinuation of, or any other change in a concomitant medication, therapy or treatment)

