4.6.3 Patient Characteristics

The following patient characteristics at baseline will be summarized by treatment group for all mITT patients:

- Demographic (age, gender, ethnic origin, height, weight, BMI)
- Medical history and Pre-existing condition

Medical history and pre-existing conditions will be summarized by preferred term (PT) within system organ class (SOC). Medical history is defined as illness(es) that ended prior to the signing of informed consent. Pre-existing conditions and AEs at baseline are those AEs occurring during the baseline/screening visits that are Visits 1 and 2.

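### From consent to first dose, no formal SAE recording rule covers patients who are later randomised, although the screening endoscopy and biopsy fall in that window

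*Protocol*

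**What the plan says.** Protocol Section 8.5.4 sets one start for both kinds of event: "All AEs and SAEs will be collected and recorded from the time of the patient receives the first dose of study drug". The definition in Section 8.5.1 is tied to dosing in the same way: "This includes any newly occurring event or previous condition that has increased in severity or frequency since the administration of study drug". The AE row of the Schedule of Assessments (Section 1.3) is empty at Visit 1 and filled from Visit 2. The screening procedures in Section 7.1 list no AE recording.

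Section 7.1 also says what happens before dosing. On timing: "Patients will be screened within 28 days prior to baseline and administration of study medication". On consent: "Written informed consent must be obtained prior to performing any protocol-specific procedures, including washout of prohibited medications". The procedures then include "Endoscopy which must be evaluated by a central reader to confirm the endoscopic sub-score for the eligibility" and "Biopsy sampling for histologic assessment and tissue concentration during the endoscopy".

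Two other places assume that events are known from this period. For patients who consent but are not randomised, Protocol Section 5.4 states: "Minimal screening failure information includes demography, screen failure details, eligibility criteria, and any SAE". SAP Section 4.6.3 states: "Pre-existing conditions and AEs at baseline are those AEs occurring during the baseline/screening visits that are Visits 1 and 2".

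**The concern.** Every patient has an invasive procedure, required by the protocol, before AE and SAE collection opens. Some may also stop a prohibited drug in that period. If a serious complication follows and the patient still goes on to randomisation, the protocol does not tell the site to record it as an SAE, grade it or follow it up. Whether it has to be reported then depends on whether the patient is later randomised, which has nothing to do with the harm.

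Two things are at stake. The first is participant protection: safety is part of the primary objective, and the risk of study-required procedures should be documented for all who undergo them. The second is interpretation: if an event present before dosing continues afterwards, the judgement that it has worsened needs a pre-dose severity, and the plan does not ask for one.

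**Working it through.** No statistical calculation applies, so the check sets the rules side by side.

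**1. Which rule reaches a serious complication that arises after consent and before first dose?**

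| Patient's later path | Section 5.4 (screen failures) | Section 8.5.4 (from first dose) | Result |
|---|---|---|---|
| Not randomised | Applies; any SAE is required | Never opens; no dose is given | Covered |
| Randomised and dosed | Does not apply | Not yet open when the event occurs | No formal rule |
| Randomised, never dosed | Does not apply | Never opens | No formal rule |

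**2. Does any other text move the start of collection?**

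- Section 8.5.4 closes by referring to subjects who have given informed consent. That says whose events are collected, not from when.
- Section 10.7 sends SAEs to the Safety Monitoring Committee throughout the study period. It governs routing, and that period is not defined.
- Section 7.2.1 has medical history confirmed at Visit 2. This may note a condition, but it is not SAE reporting.
- The Schedule and Section 7.2.1 do include AE recording at Visit 2. Under Section 8.5.4, only events from the first dose onward fall within it.

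**3. Where would the SAP's baseline AEs come from?** At Visit 1 the protocol records none. At Visit 2 the events inside the collection window are those from first dose onward, and SAP Section 4.8.1 already classes these as treatment-emergent. SAP Section 4.6.3 limits medical history to illness that had ended before consent, so by that definition it does not cover events arising between consent and first dose. The Visit 1 part of the category therefore has no AE source in the protocol.

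**4. Do the protocol's own visit lists agree?** No. The Safety Assessments list in Section 1.2 and the Schedule start AE recording at Baseline. The list in Section 8.2 starts at Week 4.

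**5. Size.** Endoscopy with biopsy is scheduled twice per patient, at Screening and at Week 8. With full enrolment and no early termination:

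- scheduled endoscopies in randomised patients: 48 × 2 = 96
- of these, before first dose: 48 × 1 = 48
- share outside AE and SAE collection: 48 / 96 = one half

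The uncovered time is at most 28 days per patient. The documents give no complication rate, so no expected number of events can be derived.

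**The case against.** The strongest reply is that little is truly lost. Medical history is taken at Visit 1 and confirmed at Visit 2. Listing 16.2.4.2 in the SAP shells holds onset and resolution dates and allows an ongoing status, and Table 14.1.3 summarises medical history and pre-existing conditions together. A screening complication therefore has somewhere to appear. A reader might infer that such an event vanishes once the patient is randomised. The documents do not support that: what is absent is formal AE and SAE recording, not every possible trace.

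A reader might also infer that Sections 5.4 and 8.5.4 contradict each other. They do not in the strict sense. Section 5.4 concerns only patients who are never randomised and is not breached in anyone else, so a site can follow both. They are inconsistent windows for the same kind of event.

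A third tempting inference is that treatment emergence cannot be judged. That goes too far. Section 8.5.4 requires an onset date for each event. Vital signs are taken at both pre-dose visits. Physical examination, ECG and laboratory tests are done at screening, and again at baseline unless screening was within 10 days. Most events can be classified from these. What remains is narrower: an event from screening that continues after dosing has no required pre-dose severity against which to call it worse.

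Finally, the washout exposure is limited. The 60-day exclusion for biologics and tofacitinib (Section 5.2) cannot be run in full within a 28-day screening period, whereas the 2-week exclusions for rectal therapy and intravenous corticosteroids can. This narrows the washout part of the point. The endoscopy and biopsy, which apply to every patient, are untouched by it.

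**Conclusion.** The point holds as a gap in safety recording. For a patient later randomised, whether or not dosed, the protocol has no formal SAE rule between consent and first dose, and the SAP's Visit 1 AE category has no protocol source. The gap lasts up to 28 days and takes in one of the two scheduled endoscopies with biopsy for each of up to 48 patients. Both figures are ceilings: enrolment may be smaller and screening shorter.

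The effect is on the completeness of the safety record and, to a limited degree, on judging whether a pre-dose event worsened. The primary endpoint and the efficacy analyses are not affected, and the treatment-emergent tables properly start at first dose.

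The conclusion assumes that Section 8.5.4 is followed as written and that no document outside the protocol and SAP, such as eCRF completion instructions, opens collection at consent. If one does, the remaining task is to make the protocol say so.

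**What to change.** - Amend Protocol Section 8.5.4 to collect all SAEs, and AEs related to study procedures or washout, from signed consent. All other AEs can still start at first dose.
- Bring the related text into line: the Safety Assessments list in Section 1.2, the Schedule in Section 1.3, the screening procedures in Section 7.1, the visit list in Section 8.2 and the AE definition in Section 8.5.1.
- Add a relationship-to-procedure field. Section 8.5.3.2 grades relationship to study drug only, so opening the existing AE page earlier would not capture it.
- In the SAP, keep the treatment-emergent tables starting at first dose and list pre-dose events separately. That gives the baseline category in Section 4.6.3 a defined source.

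The cost is a protocol amendment touching several sections, a minor eCRF change and slightly more data entry at screening. No analysis of the primary endpoint changes.

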#### 8.5.5 Reporting Events to Patients

Not applicable.

#### 8.5.6 Events of Special Interest

Not applicable.

#### 8.5.7 Reporting of Pregnancy

Serum pregnancy testing will be conducted for all female patients with child-bearing potential at screening and all treatment visits. If a female patient becomes pregnant during clinical study, the investigator should prepare and submit an initial pregnancy report to the Sponsor within 24 hours of becoming aware of the pregnancy. The investigator should follow up and document all progresses and results of pregnancy, even if the patient withdraws consent or terminate the clinical study. In addition, the investigator should prepare and submit the pregnancy outcome report within 24 hours of becoming aware of all results of pregnancy.

Pregnancy itself is not considered as an AE if the pregnancy is not related to the investigational product.

All SAEs that occur during pregnancy will be recorded in an SAE report and the reporting will be performed according to the SAE reporting procedures.

## **9 STATISTICAL CONSIDERATIONS**

The statistical analysis of the data obtained from this study will be the responsibility of the CRO. Details of the statistical analyses will be included in a separate statistical analysis plan (SAP) which will be finalized before the first individual unblinding. If, after the study has been unblinded, changes are made to the pre-specified statistical analysis plan, the changes will be listed along with an explanation as to why they occurred in the Clinical Study Report.

### **9.1 General Methodology**

No formal inferential statistical analyses are planned. Rather, for the quantitative endpoints (efficacy, biomarker measure, and some safety data) descriptive statistics will be calculated to provide an indication of directional changes in endpoints for each treatment group. For the qualitative data, frequency counts and incidence rates will be compiled for each treatment group.

Summary of tabulations will be presented by treatment group displaying the number of observations, mean, standard deviation, median, minimum, and maximum for continuous variables, and the number and percent per category for categorical data.

